4. STUDY AIMS AND OBJECTIVES

This study will be delivered in two sections: Part A and Part B. The aim of Part A is to assess whether intensive home monitoring of creatinine is an acceptable and feasible form of monitoring for patients. Part B of the study will aim to show earlier detection of deteriorating kidney function and AKI as compared to standard of care renal monitoring.

Table 2: Study objectives, outcomes and measures

Objectives	Outcome Measures	Timepoint(s) of evaluation of this outcome measure (if applicable)
Primary Objectives		
Part A: To evaluate patient acceptance of intensive home-monitoring of whole-blood creatinine.	Questionnaire and interview Absolute number of creatinine readings received-expected vs actual Time sample taken vs. time expected to take Value sent/received vs. value on device (when downloaded at the end of the study period)	Week 4
Part B: To evaluate the potential for earlier diagnosis of AKI/change in renal function with intensive home-monitoring of whole-blood creatinine.	Time from beginning of current cycle treatment to detection of AKI by amended algorithm or clinician/laboratory reading Severity of AKI at detection (as	Throughout study period
	per Kidney Disease Improving Global Outcomes AKI Work Group staging) Overall change in renal function from beginning to end of study period	

Secondary Objectives		
Part B: To assess whether intensive monitoring influences the change in kidney function over the study period compared to standard of care	Comparing kidney function at the beginning and end of the study	Weeks 1 and 6
Part B: To assess whether home monitoring of kidney function has a positive impact on a patient's quality of life.	Medical outcomes study short form 36 (SF-36) questionnaire	Week 6
Part B: To evaluate the adherence of patients to intensive home monitoring regimen	Absolute number of creatinine readings received Time sample taken vs. time expected to take Value sent/received vs. value on device (when downloaded at the end of the study period)	Week 6
Exploratory Objectives		
Part A: Using data gathered to improve and test amended AKI algorithm	Amended algorithm outcome vs clinician assessment Feedback and analysis from interviews and questionnaires	On completion of Part A
Part B: To explore the value of novel renal biomarkers in the cancer population for early detection and monitoring of AKI.	Urine and serum analysis	Throughout study period

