5.2 Part B

If, following Part A, the process is found to be an acceptable form of monitoring to patients, the study will continue to Part B. This will evaluate the potential for earlier diagnosis of AKI with intensive home monitoring of kidney function (plus standard of care monitoring) compared with standard of care only. The decision of whether to proceed to this stage of the study is described in further detail below. Participants who have been recruited to Part A of the study can continue to Part B if they so wish (and will be randomised).

Part B will enrol 60 patients being treated for cancer with potentially nephrotoxic anti-cancer therapies, randomised to either the intensive monitoring (device) group or the standard of care monitoring group, in a 1:1 ratio. Participants in both groups will be asked to complete a quality of life questionnaire at baseline. Both groups will receive standard of care monitoring of kidney function. In addition, participants in the intensive monitoring group will upload their creatinine reading three times per week (Mon/Wed/Fri) for 6 weeks. As in Part A, participants in the intensive monitoring group will be required to access the app on their own compatible device and upload their readings over their own internet connection. In both study arms, in line with scheduled clinic appointments (weeks B1, B3 and B6), blood and urine will be collected for exploratory biomarker analysis, along with renal function and cystatin C. When a participant attends a clinic appointment, a creatinine reading will be taken (either by the study participant or by a member of the study team) using the device, for comparison with the laboratory reading of creatinine taken that day.

During Part B of the study, when a participant has submitted their creatinine reading they will receive a successful submission message on the app and may receive feedback based on their reading (this depends on feedback from Part A of the study, performance of the amended algorithm from Part A and development of the smart phone application). As with Part A, participants will be directed to their

parent medical team if there is concern over their reading. Creatinine readings and AKI alerts from the algorithm will also be reviewed by the Chief Investigator once a week and highlighted to the parent medical team if there are concerns.

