1.3 Format and scale of the data

Approximately 20 creatinine readings per study participant captured in encrypted electronic form. Baseline data capture in paper workbook and consolidated into excel workbook

Participant feedback from paper-based questionnaires.

Approximately 72 participants to be recruited (30 will be randomised in to the non-device group therefore will not be sending in creatinine readings)

2. Data collection / generation

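### Part B's time-to-AKI measure lets an unconfirmed algorithm alert count as AKI, and in effect only the device arm can generate such alerts

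*Protocol*

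**What the plan says.** Table 2 in Protocol section 4 lists three primary measures for Part B. The first is time from the start of the current treatment cycle to "detection of AKI by amended algorithm or clinician/laboratory reading". The second is "Severity of AKI at detection", by KDIGO staging. The third is overall change in renal function over the study period.

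Section 5.2 gives the two arms different data streams:

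- Device arm: "participants in the intensive monitoring group will upload their creatinine reading three times per week (Mon/Wed/Fri) for 6 weeks".
- Both arms: "Both groups will receive standard of care monitoring of kidney function", at a frequency the protocol does not give, plus study samples: "In both study arms, in line with scheduled clinic appointments (weeks B1, B3 and B6), blood and urine will be collected".
- Control arm: the Data Management Plan (appendix 14.5, item 1.3) says "30 will be randomised in to the non-device group therefore will not be sending in creatinine readings".

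Section 3.7 and the Part A design section describe the algorithm as running on readings sent in through the app. On alerts in Part B, section 5.2 says "AKI alerts from the algorithm will also be reviewed by the Chief Investigator once a week". Nothing requires a laboratory value to confirm an alert before it counts as AKI, and nothing applies the amended algorithm to control-arm values.

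**The concern.** The clinician/laboratory route to an AKI event is open to both arms. The amended-algorithm route is in effect open to one. An alert caused by measurement error or a passing fluctuation would then be recorded as early AKI in the device arm, with no counterpart in control.

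The protocol gives reasons to expect some false alerts. Section 3.7 says the algorithm was amended for practical reasons. Testing it against clinician assessment is only an exploratory aim, in the 12 patients of Part A. Section 7.2 says the Part A device is intended for use by health professionals in hospital, and that the Part B device may change. The participant booklet tells people that day-to-day variation is normal.

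At stake is the claim in section 3.8 of clinical benefit through time to diagnosis. As the measure is worded, a positive result could mean earlier diagnosis of the same AKI, extra events that are not AKI, or a mixture.

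**Working it through.** **The plan's own figure.** There is none for this measure. The Part B sample size in section 9 rests on mean creatinine (1.2 against 0.9 mg/dl, SD 0.2), not on AKI detection.

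**Is the algorithm route confined to one arm?** This is inferred, because no sentence says so outright. Uploaded readings feed the algorithm (section 3.7; Part A design), device-arm participants upload (section 5.2), and the other 30 send nothing (appendix 14.5). The one possible exception is the clinic-day device reading: "When a participant attends a clinic appointment, a creatinine reading will be taken". Its arm is not specified, but its stated purpose is comparison with the laboratory value, and it is not said to feed the algorithm.

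**Inputs from the documents.** 60 participants randomised 1:1, so 30 per arm. Home readings: 3 × 6 = 18 in the device arm, 0 in control.

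**Assumptions, because the documents give no figure.** True AKI 20% in each arm, with onset uniform over six weeks. Six weekly laboratory tests in both arms, which alone date true AKI, so there is no real benefit. A false-flag probability *p* per test, the same for home readings and laboratory tests, independent between tests.

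**Step 1: participants counted as having AKI.** The device arm has 18 + 6 = 24 opportunities for a false flag and control has 6. The proportion counted is 1 − 0.8(1 − *p*)^24 against 1 − 0.8(1 − *p*)^6.

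| *p* | Device arm | Control arm |
|---|---|---|
| 0.5% | 1 − 0.8 × 0.887 = 29% | 1 − 0.8 × 0.970 = 22% |
| 1% | 1 − 0.8 × 0.786 = 37% | 1 − 0.8 × 0.941 = 25% |
| 2% | 1 − 0.8 × 0.616 = 51% | 1 − 0.8 × 0.886 = 29% |

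The true figure is 20% in both.

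**Step 2: effect on a time-to-event comparison.** The protocol does not name a log-rank test (section 9 names a t-test and ANOVA); it is used here as a natural test for a time to detection. Share of simulated trials significant at two-sided 5%:

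| *p* | Same false-flag rate on home and laboratory tests | Laboratory tests error-free |
|---|---|---|
| 0.25% | about 6% | – |
| 0.5% | about 9% | 10–11% |
| 1% | 19–20% | 22–23% |
| 2% | 43–45% | 56–58% |

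With no false flags the rate is about 5%, as it should be. At the rates of 0.5% and above, virtually all significant results point to earlier AKI in the device arm. The first column is the fairer one, because it does not assume a perfect control measurement.

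**Step 3: stage at detection.** This is defined only in people with a detected AKI, so the groups compared are not the randomised groups. Two mechanisms can lower it in the device arm without benefit. One is marginal alerts that add low-stage cases. The other is lead time: for uniform onset, the mean wait to the next test is Σg²/(2Σg), where g is the gap between tests. Monday/Wednesday/Friday gives (4 + 4 + 9)/14 = 1.2 days, and an assumed weekly test gives 49/14 = 3.5 days. The same rising creatinine is then staged at an earlier point on its course.

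**The case against.** The strongest reply is that more frequent testing is the intervention and earlier diagnosis the stated aim. That stands: a shorter time to true AKI is the effect sought. The point is confined to alerts that are not AKI but are counted as AKI.

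It can also be said that Part A tests and is meant to improve the algorithm, that clinic-day readings are compared with the laboratory, and that section 10.1 calls this a feasibility study. These are useful checks, but none alters what counts as an event in Part B, and the progression factors in section 5.3 are recruitment and adherence, not algorithm accuracy. Detailed dating rules may sit in an analysis plan not seen here; the event definition itself is in the protocol.

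Four stronger readings are tempting and not supported:

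- *Nobody sees an alert until the weekly review.* Section 5.2 says participants will be directed to their medical team if a reading causes concern, may receive app feedback, and that the weekly review is additional. The booklet describes weekly review without contact, so some delay is possible, but no fixed delay can be derived for Part B.
- *Controls can be detected only at the three study visits.* They also receive standard-care monitoring of unstated frequency. Section 3.5 says unexpected events prompt checks, and section 3.4 says the NHS recommends a standard algorithm in hospital laboratory systems.
- *False alerts must lower average severity.* A grossly wrong reading would be staged high. Severity can be lowered; it need not be.
- *The whole of Part B is uninterpretable.* Overall change in renal function does not use the algorithm, and the sample size rests on creatinine.

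**Conclusion.** The concern holds for the two AKI measures. As Table 2 is worded, an unconfirmed alert counts as AKI detection, and in effect only the device arm can produce one. With identical true AKI and no benefit, the chance of a significant log-rank result rises from about 5% to about 9%, 19–20% and 43–45% at false-flag rates of 0.5%, 1% and 2% per test. At 0.25% the inflation is slight, at about 6%.

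These sizes depend on the assumed false-flag rate, 20% AKI, weekly laboratory testing and independent errors. The direction of the distortion does not depend on the exact values, provided some false alerts occur. Device-only use of the algorithm is an inference, though a well-supported one. Stage at detection can also favour the device arm through lead time or marginal alerts. The third primary measure is unaffected.

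**What to change.** Change the outcome wording in Table 2 before Part B starts:

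1. Count AKI in both arms only when a laboratory creatinine, from a routine or planned study sample, meets the same KDIGO-based criterion.
2. In the device arm, let an alert set the detection date only if a laboratory value confirms it within a pre-specified window. Use the date the alert reached the participant's medical team or a reviewer. Without the window, a false alert followed weeks later by unrelated AKI would still count as early detection.
3. Otherwise, in both arms, use the date the laboratory or clinician result was known.
4. Report unconfirmed alerts separately as a false-alert rate.
5. Keep stage at detection as descriptive, and add worst laboratory stage (0 to 3) over follow-up in all randomised participants. The two answer different questions.

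The study visit weeks also need reconciling, because they determine when planned confirming samples exist: section 5.2 gives B1, B3 and B6, and Table 4 gives weeks 1, 4 and 8.

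The cost is small: revised wording, a chosen window, and recording when each alert was seen. No extra participants are needed, and the samples are routine or already planned. The downside is that brief true AKI which resolves before a laboratory sample is not counted in the primary measure; it would appear only among the unconfirmed alerts.

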7. STUDY PROCEDURES

Once a patient has agreed to take part in the study and informed consent is gathered the following will be gathered from medical records and the patient:

- 1. Baseline kidney function urea, creatinine and eGFR at point of diagnosis and 3 months previous
- 2. Significant past medical and surgical history
- 3. Previous cancer treatments relating to incident cancer diagnosis
- 4. Risk factors for AKI
- 5. Blood pressure at previous clinic attendances relating to incident cancer diagnosis
- 6. Urine collection and dipstick results at previous clinic attendances relating to incident cancer diagnosis
- 7. Concomitant medication and recent acute prescriptions

Table 3: Trial Procedures Part A

Procedures – Part A	Visits			
	Screening	Baseline Week 1 (+-1 week)	Week 2 (+- 1 week)	Week 4 (+- 1 week)
Informed consent	х			
Demographics (from medical notes)		х		
Medical history (from medical notes)		х		
Phone call		х		
Blood Pressure		х		Х
Urine Collection		х		Х
Blood Collection		х		Х
Usability Questionnaire				х
Workbook completion		х		х
Semi-structured interview				х

Table 4: Trial Procedures Part B

^{* -} intensive monitoring group only

Procedures - Part B	Visits			
	Screening	Baseline Week 1 (+-1 Week)	Week 4 (+- 1 week)	Week 8 (+- 1 week)
Informed consent	х			
Demographics (from medical notes)		x		

Medical history (from medical notes)	х		
Phone call*	x		
Blood Pressure	X	Х	х
Urine Collection	X	Х	х
Blood Collection	Х	Х	Х
Usability			x
Questionnaire*			
QoL Assessment	X		х
Workbook completion	X	Х	Х
Semi-structured interview – participant*			х
Clinician interview			x

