9. STATISTICAL CONSIDERATIONS AND DATA ANALYSIS

For Part A of the study, a powered sample size calculation has not taken place. In line with published recommendations³¹ 12 patients will be recruited to receive the StatSensor® to assess the general process of taking creatinine readings and sending in results via the app. Descriptive statistics will be used to summarise demographic data and clinical variables. Categorical data will be reported using frequencies and percentages. Quantitative variables will be reported using either the mean and standard deviation or the median and interquartile range depending on the distribution of the data. The standard error of the mean will also be calculated.

For Part B current powered sample size calculations estimate 30 study participants to be satisfactory. This number will be sufficient as overall creatinine levels will be used as an end point for higher statistical power as well as AKI rate. A Student's t-test and one-way ANOVA test will be used to analyse data for statistical significance.

The significance has been calculated using the assumption during standard treatment for head and neck cancer, the mean creatinine readings are 1.2 +/- 0.2 mg/dl, with closer monitoring having the potential to bring it down to 0.9+/-0.2 mg/dl based on the results of docetaxel, cisplatin, and 5-fluorouracil therapy³².

Themes from the interviews will be developed and analysed in more detail in line with published guidance on qualitative study analysis³³.

Analysis of data from this study will be in conjunction with the statistics department of the sponsor and in-house statistician support and other statistical analyses will be used as appropriate.

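### Part B tests creatinine by t-test and one-way ANOVA with no baseline covariate; ANCOVA on baseline laboratory creatinine would be more precise with the same patients and samples

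*Protocol*

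**What the plan says.** Protocol Section 4, Table 2, lists "Overall change in renal function from beginning to end of study period" among the primary outcome measures for Part B. A secondary row, timed at weeks 1 and 6, is worded "Comparing kidney function at the beginning and end of the study".

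Section 9 describes the same quantity as a level rather than a change: "overall creatinine levels will be used as an end point for higher statistical power as well as AKI rate". Its planning figures are also levels: "the mean creatinine readings are 1.2 +/- 0.2 mg/dl, with closer monitoring having the potential to bring it down to 0.9+/-0.2 mg/dl". For the test, it says that a Student's "t-test and one-way ANOVA test will be used to analyse data for statistical significance". No covariate is named. The section ends by allowing other analyses where appropriate, without naming one.

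Section 5.2 plans blood sampling with renal function in both arms at weeks B1, B3 and B6, and refers to a laboratory creatinine on the day of a clinic visit. Section 7 adds values taken from the notes: "urea, creatinine and eGFR at point of diagnosis and 3 months previous".

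**The concern.** The named tests do not fit this outcome well, for two reasons.

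First, Part B has two arms. One-way ANOVA by arm is then the t-test again (F = t²) and adds nothing.

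Second, the protocol does not say whether the t-test is applied to change, as in Table 2, or to levels, as in Section 9. The two have different variances, and in most realistic settings both are less precise than an analysis of the end value adjusted for the baseline value. Patients start treatment with different creatinine levels, eligibility sets no renal-function limit, and Section 5.4 names no stratification. With 30 per arm, a chance difference at baseline is therefore possible, and neither form of the t-test handles it fully.

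At stake is precision, and robustness to that imbalance. The validity of the randomised comparison is not in question.

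**Working it through.** **Inputs.** Means 1.2 and 0.9 mg/dl, so a difference of 0.3, with SD 0.2 (Section 9, reading the ± as an SD). Enrolment: "Part B will enrol 60 patients being treated for cancer with potentially nephrotoxic anti-cancer therapies", randomised 1:1 (Section 5.2), so 30 per arm. The correlation ρ between baseline and end-of-study creatinine is not in the documents; a range is used. The formulas assume equal SDs at both times and a linear relation.

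**The plan's own figure.** Section 9 says: "For Part B current powered sample size calculations estimate 30 study participants to be satisfactory". It does not say whether this is per arm or in total, and gives no alpha, sidedness or power, so it can be neither confirmed nor refuted. At two-sided 5%, a t-based calculation on the stated inputs gives totals of 18, 22, 26 and 36 for 80%, 90%, 95% and 99% power. Fifteen per arm gives about 98% power.

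At 30 per arm, SE = 0.2 × √(2/30) = 0.0516, and 0.3/0.0516 = 5.81. Power is Φ(5.81 − 1.96) = Φ(3.85), above 99.9%.

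**Variance relative to a t-test on final values.**
- Change score: 2(1 − ρ).
- ANCOVA: 1 − ρ², times 1 + 1/(2n − 4) = 1 + 1/56 = 1.018 for the lost degree of freedom at n = 30 per arm.
- ANCOVA against change, before that factor: (1 − ρ²)/[2(1 − ρ)] = (1 + ρ)/2.

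| ρ (assumed) | ANCOVA / final | ANCOVA / change | SE in mg/dl: final, change, ANCOVA |
|---|---|---|---|
| 0.5 | 0.75 | 0.75 | 0.0516, 0.0516, 0.0451 |
| 0.7 | 0.51 | 0.85 | 0.0516, 0.0400, 0.0372 |
| 0.8 | 0.36 | 0.90 | 0.0516, 0.0327, 0.0313 |
| 0.9 | 0.19 | 0.95 | 0.0516, 0.0231, 0.0227 |

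The SEs include the 1.018 factor; the ratios do not. With the factor, ANCOVA beats the change score when 1.018(1 + ρ)/2 < 1, that is ρ below about 0.96. It beats the final-value test when 1.018(1 − ρ²) < 1, that is ρ above about 0.13.

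**What this buys.** The difference detectable with 80% power (two-sided 5%, 30 per arm) for final value, change and ANCOVA is 0.147, 0.147 and 0.129 mg/dl at ρ = 0.5, and 0.147, 0.114 and 0.106 at ρ = 0.7. All are well under 0.3. If the true difference were 0.1 mg/dl (an assumption), power would be 49%, 49% and 61% at ρ = 0.5, and 49%, 71% and 77% at ρ = 0.7 (normal approximation, without the 1.018 factor).

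**Chance imbalance.** With SD 0.2, the baseline difference between arms also has SE 0.0516, so its 95% range is ±1.96 × 0.0516 = ±0.10 mg/dl, a third of the planned 0.3. Given a baseline gap d, the final-value comparison is shifted by ρd and the change score by −(1 − ρ)d; ANCOVA removes the shift. At ρ = 0.7 and d = 0.10, these are 0.7 × 0.10 = 0.07 and −0.3 × 0.10 = −0.03 mg/dl.

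**The case against.** The strongest reply is that a t-test on change already uses baseline. This stands: it would be wrong to say that the plan ignores baseline if the Table 2 definition is followed. The gain is then 5% to 25% of variance for ρ from 0.9 to 0.5, and smallest where creatinine is most stable within a person. The larger gain applies only to the levels reading, which Section 9 suggests but does not settle.

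It also stands that power is already above 99.9% on the protocol's own inputs. And covariates, scale and analysis sets often belong in a SAP, which is not at hand. But this protocol does name its tests, and the clause allowing other analyses commits to nothing.

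A reader might infer more than the documents support:

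- **Home meter readings pooled into the arm comparison.** The phrase about overall creatinine levels could suggest this, and only the device arm has home readings. No section plans such an analysis. Section 5.2 provides renal function in both arms, and the data management plan (Section 14.5) says that devices were calibrated with the hospital laboratory. Any figure for meter bias would be invented.
- **One-way ANOVA run across repeated visits as if values were independent.** No section says so. By arm, the test is redundant and harmless.
- **A pre-randomisation laboratory baseline already in hand for everyone.** Table 4 lists only consent at screening. Blood collection starts at week 1 with a one-week window either side, and its order relative to randomisation and the first home reading is not stated. The values from diagnosis and three months earlier may be remote from randomisation.

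**Conclusion.** The point holds as an improvement in efficiency. The protocol names two tests that are one test for two arms, leaves open whether it acts on change or on level, and adjusts for nothing, although renal function is planned at the start and end in both arms. ANCOVA would have 0.75 to 0.95 of the variance of a change-score t-test for ρ of 0.5 to 0.9, or 0.75 to 0.36 of that of a final-value t-test for ρ of 0.5 to 0.8, less about 2% for the degree of freedom. These sizes rest on an assumed correlation and on equal SDs at both times.

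The gain would hardly change the result if the true difference is near 0.3 mg/dl. It matters if the difference is nearer 0.1, and as protection against baseline imbalance. It does not show that the trial is too small or that the named test is invalid.

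**What to change.** In Section 9, replace the t-test and one-way ANOVA for this outcome with ANCOVA of end-of-study laboratory creatinine on arm and baseline laboratory creatinine, reported as an adjusted difference with a 95% confidence interval. A log scale is optional and would give an adjusted ratio. State that the comparison between arms uses laboratory values, and use the same outcome definition in Table 2 and Section 9.

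Two things must be settled first:

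- **Baseline.** Define it as the B1 laboratory value, taken before randomisation or at least before the first home reading.
- **Final visit.** Table 2 and Section 5.2 put it at week 6, and Table 4 in Section 7 at week 8. These must be reconciled before an end-of-study value can be defined.

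The cost is wording, one degree of freedom, and possibly a small clarification of when the B1 sample is drawn and recorded. No extra patients or samples are needed.

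### The Part B kidney-function comparison uses only first and last values, so a participant with a mid-study laboratory result but no end sample may contribute nothing; a repeated-measures model with the end-of-study contrast would use that result

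*Protocol*

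**What the plan says.** Section 5.2 sets the sampling: "In both study arms, in line with scheduled clinic appointments (weeks B1, B3 and B6), blood and urine will be collected", and this is done "along with renal function and cystatin C". Table 4 in section 7 also has three blood collections, but at weeks 1, 4 and 8.

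Section 4, Table 2, defines the Part B kidney-function outcome twice, each time from two points:

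- Primary objective: "Overall change in renal function from beginning to end of study period". The timepoint entry for the row as a whole covers the entire study period.
- Secondary objective: "Comparing kidney function at the beginning and end of the study", with weeks 1 and 6 as the only timepoints.

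Section 9 states that "overall creatinine levels will be used as an end point for higher statistical power as well as AKI rate", without saying whether this means a change, an end value or an average. It names Student's t-test and one-way ANOVA, and leaves room for other analyses as appropriate.

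Section 6 says that on withdrawal, permission will be sought to use data already collected and routine-care data for the rest of the study period.

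**The concern.** A two-point change compared by t-test can only use people who have both points. Some participants may be too unwell to give an end sample or may withdraw; section 6 itself lists loss of capacity or ability as a reason for withdrawal. For those who had already given the mid-study sample, a laboratory result from the same trial is on file and the stated comparison does not use it.

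Two things are at stake. One is precision for the end-of-study difference. The other is bias. An analysis of those with an end value is valid only if, given arm (and baseline, where adjusted for), having an end sample is unrelated to what that sample would have shown. Deteriorating kidney function is a plausible reason for not reaching the end visit, and the mid-study creatinine is the observed variable most likely to reveal it.

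This is not a complaint that the protocol lacks analysis-plan detail. Table 2 fixes the timepoints and section 9 names the tests, and together they leave the middle value out.

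**Working it through.** **Inputs from the protocol.** "Part B will enrol 60 patients being treated for cancer with potentially nephrotoxic anti-cancer therapies", randomised 1:1, so 30 per arm (section 5.2). Assumed means are 1.2 and 0.9 mg/dl, a difference of 0.3, with SD 0.2 (section 9). Post-baseline laboratory visits: two.

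**Inputs assumed.** Correlation r between visits: 0.5 to 0.9. Correlation pattern: equal between all visits, or first-order decay. Fraction m missing the end value but having the middle one: 15%, with 10–30% as a range. The documents give none of these.

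**1. The plan's own figure.** Section 9 says "current powered sample size calculations estimate 30 study participants to be satisfactory", without alpha, power or whether 30 is a total or per arm, so it cannot be reproduced uniquely. With n per arm = 2(z₁ + z₂)²(SD/difference)², two-sided 0.05:

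- 80% power: 2 × 7.85 × (0.2/0.3)² = 6.98, so 7 per arm (9 with the t distribution).
- 90% power: 10 per arm (11 with the t distribution).
- Read as 15 per arm, 30 gives 97.7% power by the t distribution; read as 30 per arm, over 99.9%.

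**2. Does losing end values threaten power?** From 30 per arm, t distribution, SD 0.2 as given:

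| End values missing | n per arm | Power for 0.3 mg/dl | Difference detectable at 80% power |
|---|---|---|---|
| 0% | 30 | 99.99% | 0.147 mg/dl |
| 10% | 27 | 99.97% | 0.155 |
| 20% | 24 | 99.91% | 0.165 |
| 30% | 21 | 99.73% | 0.177 |

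For the assumed effect the answer is no.

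**3. What the middle value adds to the end contrast.** Both analyses adjust for baseline, so only the use of the middle value differs. Let q be the correlation between middle and end values given baseline. Set the variance of the end-visit arm difference with complete data to 1.

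- Complete cases: 1/(1 − m).
- Mixed model using the middle value: (1 − q²)/(1 − m) + q².
- Ratio of the second to the first: 1 − m·q².

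At m = 0 the ratio is 1, so there is no gain with complete data.

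With equal correlation, q = r/(1 + r). With first-order decay, q = r/√(1 + r²). At m = 0.15, complete cases give 1/0.85 = 1.176, and:

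| Pattern | r | q² | Mixed model | Reduction, m·q² |
|---|---|---|---|---|
| Equal | 0.5 | 0.111 | 1.157 | 1.7% |
| Equal | 0.9 | 0.224 | 1.137 | 3.4% |
| Decay | 0.5 | 0.200 | 1.141 | 3.0% |
| Decay | 0.9 | 0.448 | 1.097 | 6.7% |

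The reduction is therefore about 2–7%. In effective numbers per arm, complete cases give 0.85 × 30 = 25.5, and the mixed model gives 30/1.157 = 25.9 to 30/1.097 = 27.3. For 10%, 20% and 30% missing, the reductions are about 1–4.5%, 2–9% and 3–13%.

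**4. Averaging the two follow-up values instead.** With change scores and equal correlation, the variance is 2(1 − r) for one follow-up and 1.5(1 − r) for the mean of two, a 25% cut at any r. This answers a different question. If the effect at the middle visit is a fraction x of the end effect, the averaged effect is (1 + x)/2 of it. Averaging wins only if (1 + x)/2 > √0.75, that is x > 0.73. If the effect builds linearly from week 1, x = (3 − 1)/(6 − 1) = 0.40 on weeks 1/3/6, or 3/7 = 0.43 on weeks 1/4/8. At 0.40 the averaged effect is 0.70 of the end effect and relative efficiency is 0.70²/0.75 = 0.65, so 30 per arm acts like about 20.

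**The case against.** The strongest case against is that a beginning-to-end change is a legitimate endpoint, and preferring a longitudinal model is a matter of taste. The protocol leaves other analyses open and involves the sponsor's statisticians, and a covariance structure normally belongs in an analysis plan. The wording about overall creatinine in section 9 could already cover every visit. A middle laboratory value can also feed the AKI detection outcome, so it is not wasted.

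Much of this stands. The omission is clear in Table 2 but not in section 9, and it concerns the change measure only. What does not fall away is that the timepoints and tests which are stated give the middle value no part in that measure; an open clause prespecifies nothing.

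A reader might infer three stronger points that the documents do not support:

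- **That everyone without an end sample is excluded.** No such rule is stated. It is an inference from a two-point comparison, and section 6 may supply routine laboratory values after withdrawal where permission is given and a result exists.
- **That a quarter or more of the precision is being thrown away.** That figure belongs to an average over visits. For the contrast the protocol chose, the gain is nil with complete data, and the average can be the weaker test if the effect comes late.
- **That the trial is underpowered as a result.** It is not, at the assumed difference.

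**Conclusion.** The point holds in a limited form. Part B collects a mid-study laboratory value in both arms, and the stated change comparison does not use it. A participant with that value but no end sample would contribute nothing unless a routine-care value is recovered.

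The precision at stake for the end contrast is modest and rests on the assumed 15% missing rate and on correlations of 0.5 to 0.9. It would matter only if the true difference were well below 0.3 mg/dl.

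The better reason to change is robustness: a model that includes the middle value remains valid when dropout depends on that observed value, which a complete-case comparison does not allow for. It does not help where both follow-up values are missing, nor where dropout depends on deterioration after the middle visit that no measurement captured.

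**What to change.** First reconcile the visit weeks. Section 5.2 and Table 2 point to weeks 1, 3 and 6 (Table 2 naming 1 and 6), while Table 4 has weeks 1, 4 and 8. Until they agree, the end visit has no fixed meaning. Either schedule includes a usable middle sample.

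Then, in Table 2 and section 9:

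- Analyse all scheduled post-baseline laboratory creatinine values in one mixed model for repeated measures, with arm, visit, arm-by-visit interaction and baseline creatinine.
- Prespecify the end-of-study arm difference from that model as the kidney-function result. This keeps the contrast the protocol already chose.
- Report the average over the two visits, if wanted, only as a supportive estimate, because a late effect dilutes it.
- State which of these is meant by overall creatinine in section 9.

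The cost is wording in two places. No samples, visits or participants are added.
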